The primary goal of this proposal is to determine the efficacy of tranexamic acid in reducing the rate of hematoma formation after breast reduction surgery. This will be a double-blinded, randomized controlled study. The research will be achieved by randomizing one breast in a bilateral breast reduction to receive topical tranexamic acid, while the other breast will not receive the study drug. Both the surgical team and the patient will be blinded to which side has received the study drug. The patient will then be followed for the standard postoperative period and the rate of hematoma development will be recorded. Patient demographics, comorbidities, treatment history, and surgical details will be collected from these charts and analyzed for their impact on perioperative blood loss. **We hypothesize that use of topical tranexamic acid will decrease the rate of hematoma formation and the rate of blood transfusion without increasing the incidence of deep vein thrombosis or thromboembolic events.**

b) Target Population and Recruitment Methods

Consecutive patients presenting for breast reduction mammoplasty performed by plastic surgeons affiliated with Montefiore Medical Center will be offered enrollment in the study. Potential study participants will be recruited at their preoperative consultation appointments that take place at the Hutchinson Metro Center campus. Written informed consent (detailed below) will be obtained from all participants before inclusion. As this proposal involves greater than minimal risk to patients, we will have a Data and Safety Monitoring Plan in place prior to beginning the study.

c) Inclusion and Exclusion Criteria

Inclusion criteria include: being over the age of 18 and being scheduled for reduction mammoplasty at the Hutchinson Metro Center campus of Montefiore Medical Center.

Exclusion criteria include: oncologic breast reductions, unilateral breast reductions, history of thromboembolic disease, history of bleeding diatheses, history of stroke, current pregnancy, severe comorbidity (defined as American Society of Anesthesiologists (ASA) fitness grade IV or above).

d) Primary and Secondary Outcomes

Primary outcome: development of hematoma within 30 days of surgery

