Rationale: Topical tranexamic acid has been shown to reduce perioperative blood loss and need for transfusion. A recent randomized controlled trial showed that topical tranexamic acid significantly decreased 24-hour drain output following reduction mammoplasty, though the clinical significance of this was unclear.

- *We hypothesize that breasts treated with topical tranexamic acid will have a lower rate of hematoma development compared to the contralateral control.*

Secondary outcome: incidence of blood transfusion within 30 days of surgery, incidence of deep vein thrombosis, and incidence of pulmonary embolism

Rationale: Tranexamic acid is an antifibrinolytic, and therefore acts by inhibiting fibrinolysis and stabilizing clot formation. There has historically been concern that

use of tranexamic acid will increase the incidence of thromboembolic events such as deep venous thrombosis and pulmonary embolism.

- *We hypothesize that patients treated with topical tranexamic acid will not have an increased rate of thromboembolic events compared to nationally published rates and those of our own historical controls.*

e) Study Timelines

We anticipate that data collection from the treatment arm will take 8 months and analysis and manuscript preparation will take another 4 months.

4) Study Population

a) Study Population

The study population will comprise all patients over the age of 18 scheduled to undergo breast reduction surgery at the Hutchinson Medical Center campus of Montefiore Medical Center, who meet the inclusion and exclusion criteria outlined above. No patients from before the beginning of electronic medical record use at Montefiore Medical Center will be used, as it will not be possible to explore these patients' medical records. As this proposal involves greater than minimal risk to patients, we will have a Data and Safety Monitoring Plan in place prior to beginning the study.

b) Vulnerable Populations

Include	Exclude	Vulnerable Population Type
	X	Adults unable to consent
	X	Individuals who are not yet adults (e.g., infants, children, teenagers)
	X	Wards of the State (e.g., foster children)
	X	Pregnant women
	X	Prisoners

c) Informed Consent Process

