Although creation of the data-set will require use of patient names and medical record numbers, these will be stripped as soon as data-collection is complete and a linking file will be kept under lock and key by the primary investigator. The data set will be stored on Montefiore's encrypted server. Only the study team will have access to the stored data, and only the study team will have access to the linking file. Data will be stored until the data is analyzed and scholarly output is generated. All members of the research team have undergone appropriate Human Subjects Protection training.

c) Provisions to Monitor the Data to Ensure the Safety of Subjects/Data Safety and Monitoring Plan

There will be regularly scheduled monitoring reviews by a Data Safety Monitoring Board (DSMB) at 6-month time intervals to review rates of adverse events, which will determine if the study poses sufficiently low risk to proceed. The DSMB will be comprised of two members of the Department of Surgery who are not affiliated with the study ([name], MD and [name], MD), as well as a biostatistician from the Albert Einstein College of Medicine/Montefiore Medical Center ([name], DrPH). The incidence of venous thromboembolism (VTE) in reduction mammoplasty ranges from 0.22% to 2.9%. A recent National Surgical Quality Improvement Program study describes a 0.17% rate of pulmonary embolism and a 0.07% rate of deep vein thrombosis in BRM patients.¹⁸ Furthermore, the incidence of seizure in the general population is estimated at 3%.¹⁹ With an anticipated sample size of 100 patients, if more than 2 patients (1.5%) develop either a deep vein thrombosis, pulmonary embolism, or seizure postoperatively, the study will be paused while further investigation regarding safety takes place. In the case of increased incidence of adverse events that warrant further investigation, the study will be paused and the PSF grant office will be kept apprised. We do not anticipate increased risk for thromboembolic events or seizure, given the well-described safety profile of tranexamic acid even in hypercoagulable populations such as bedbound or cancer patients, and given that we are using a low, topical dosage with fractional systemic absorption.

d) Provisions to Protect the Privacy Interests of Subjects

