We will be requesting a waiver of consent and HIPAA authorization for recruitment purposes (so as to find eligible participants for the study), but we are not seeking a waiver for the study as a whole as we are obtaining informed consent from the study participants.

e) Economic Impact on Subjects

None

7. Protocol Methodology

We have based our research strategy on that of the previously published randomized controlled trial performed by Ausen et al.¹⁶ The randomization will be performed electronically by the Albert Einstein College of Medicine Clinical Research Center. Patients will be randomized to receive topical tranexamic acid to one breast and placebo (topical saline) to the other, after obtaining hemostasis but prior to closure

during reduction mammoplasty. The study drug will be prepared and randomized with the assistance of the Einstein Investigational Drug Service as detailed below.

A custom order for the study drug will be created in Epic. Each week, the list of patients scheduled to undergo reduction mammoplasty the following week will be provided to the pharmacy. The Investigational Drug Service at Einstein will prepare randomization kits comprised of two identical 20cc syringes labeled "LEFT" or "RIGHT" based on the existing randomization table. Our pharmacy carries a standard vial of tranexamic acid at a concentration of 100mg/mL, with 10mL per vial (total 1g of TXA). We will dilute the tranexamic acid to a volume capable of moistening the typical wound surface of reduction mammoplasty; 20 mL has been shown to sufficiently moisten at least 1500cm².¹⁶ The side pre-randomized to treatment will contain 10cc of 100mg/mL of tranexamic acid diluted in 10cc of normal saline (0.9% sodium chloride). The other vial will contain 20cc of of normal saline. Tranexamic acid is colorless, therefore the two syringes will appear identical.

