Subject treatment assignments will remain blinded until the final subject has completed follow up and all data has been recorded and validated. Urgent, immediate unblinding due to medical emergency may be authorized by the Investigator. When possible, the treatment assignment will be provided to the treating physician in order to maintain the blind for the Investigator and study staff.

8. Data Analysis

We hypothesize that use of topical tranexamic acid will decrease total perioperative blood loss, hematoma formation, and transfusion rates without increasing the incidence of deep vein thrombosis or thromboembolic events.

a) Chart review data:

Patient charts will be abstracted for baseline demographic data and medical comorbidities that may independently increase the risk of developing a postoperative hematoma. Data to be abstracted from the medical record includes: demographic data (including patient gender, age, ethnicity), medical data (including body mass index, comorbidities (e.g. hypertension, diabetes, hyperlipidemia, coronary artery disease), smoking history, history of neoadjuvant radiation therapy or chemotherapy, history of thromboembolic disease, bleeding diatheses, or use of anticoagulant medications), surgical data (including type of operation performed, surgical team involved, weights of tissue removed, estimated blood loss, drain outputs in the immediate postoperative period, date that drain(s) were removed) and complications within 30 days of the index operation including hematoma requiring operative washout or bedside evacuation, seroma, cellulitis, nipple-areolar complex necrosis, fat necrosis, delayed wound healing, deep vein thrombosis and pulmonary embolism. Patients with insufficient records or those who are lost to follow-up will be excluded from the final analysis.

b) Statistical Analysis

[figure not shown]
We have partnered with our institution's Department of Surgery faculty biostatisticians on the statistical methods for this proposal. **Based on a Bayesian approach, a sample size of 100 patients will be sufficient to adequately power this study.**

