Secondary endpoints will be analyzed using classical frequentist methods, with generalized linear models used to assess treatment group difference in blood transfusion, incidence of deep vein thrombosis, and incidence of thromboembolic events.

9. Data Safety Monitoring Plan

There will be regularly scheduled monitoring reviews at 6-month time intervals to review rates of adverse events, which will determine if the study poses sufficiently low risk to proceed. The DSMB will be comprised of two members of the Department of Surgery who are not affiliated with the study ([name], MD and [name], MD), as well as a biostatistician from the Albert Einstein College of Medicine/Montefiore Medical Center ([name], DrPH). The incidence of venous thromboembolism (VTE) in reduction mammoplasty ranges from 0.22% to 2.9%. A recent National Surgical Quality Improvement Program study describes a 0.17% rate of pulmonary embolism and a 0.07% rate of deep vein thrombosis in BRM patients.¹⁸ Furthermore, the incidence of seizure in the general population is estimated at 3%.¹⁹ With an anticipated sample size of 100 patients, if more than 2 patients (1.5%) develop either a deep vein thrombosis, pulmonary embolism, or seizure postoperatively, the study will be paused while further investigation regarding safety takes place. In the case of increased incidence of adverse events that warrant further investigation, the study will be paused and the PSF grant office will be kept apprised. We do not anticipate increased risk for thromboembolic events or seizure, given the well-described safety profile of tranexamic acid even in hypercoagulable populations such as bedbound or cancer patients, and given that we are using a low, topical dosage with fractional systemic absorption.

Although creation of the data-set will require use of patient names and medical record numbers, these will be stripped as soon as data-collection is complete and a linking file will be kept under lock and key by the primary investigator. The data set will be stored on Montefiore's encrypted server. Only the study team will have access to the

stored data, and only the study team will have access to the linking file. Data will be stored until the data is analyzed and scholarly output is generated. All members of the research team have undergone appropriate Human Subjects Protection training.

10. References

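### DSMB reviews every 6 months in a trial with 8 months of data collection: only one scheduled review falls during treatment, after most patients are exposed

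*Combined protocol and SAP*

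**What the plan says.** Section 5c (Data Safety and Monitoring Plan) states: "There will be regularly scheduled monitoring reviews by a Data Safety Monitoring Board (DSMB) at 6-month time intervals to review rates of adverse events". Section 9 repeats the interval: "There will be regularly scheduled monitoring reviews at 6-month time intervals to review rates of adverse events". Both sections give the reviews a decision to make, "which will determine if the study poses sufficiently low risk to proceed".

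Section 3e (Study Timelines) states: "We anticipate that data collection from the treatment arm will take 8 months and analysis and manuscript preparation will take another 4 months".

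Section 8b says that "a sample size of 100 patients will be sufficient to adequately power this study". Under section 7, "Patients will be randomized to receive topical tranexamic acid to one breast and placebo (topical saline) to the other", so every patient is exposed, in one intraoperative application. Follow-up for the primary outcome is 30 days (section 3d).

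Sections 5c and 9 also contain two pause provisions that are not linked to a review date:

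- An event count: "if more than 2 patients (1.5%) develop either a deep vein thrombosis, pulmonary embolism, or seizure postoperatively, the study will be paused" while safety is investigated. (The bracketed percentage does not match 2 of 100. That is a separate matter and is not used here.)
- A general provision that pauses the study if adverse events increase enough to warrant investigation, with the grant office kept informed.

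Neither section says who counts events between reviews, how quickly they reach the DSMB, or whether the board takes part in the investigation after a pause.

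**The concern.** The treatment is a single application during surgery. A review that decides whether to continue can therefore protect only patients who have not yet been operated on. A calendar interval of 6 months suits a trial that accrues over years; here it nearly spans the planned treatment period.

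Sections 3b and 4a describe the study as involving greater than minimal risk and, for that reason, require a monitoring plan before it starts. Section 4c lists seizure, thromboembolism and allergic reaction as possible risks of an off-label use. The DSMB is the independent part of the monitoring plan. If its first look comes when most patients have been treated, its decision affects only a minority of those it is meant to protect.

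**Working it through.** The documents give no figure for patients exposed at a review, so there is none to reproduce.

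**Inputs from the documents.** Review interval 6 months (sections 5c and 9); data collection 8 months, then 4 months of analysis and writing (section 3e); 100 patients (section 8b), all exposed (section 7); follow-up 30 days, taken as 1 month (section 3d).

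**Assumptions not in the documents.** The review clock starts at the first surgery. Accrual is even over A months. A = 8 if the 8 months cover surgery only, with the last follow-up ending near month 9. A = 7 if the last 30-day follow-up lies inside the 8 months.

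**Step 1. Reviews during treatment.** Reviews fall at months 6, 12 and so on. Only month 6 is earlier than month 7 or 8. Month 12 equals 8 + 4, the planned end of analysis and writing. This step does not depend on the shape of accrual. A second review would fall within treatment only if accrual lasted more than 12 months.

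**Step 2. Exposure at month 6.** Exposed = 100 × 6/A. Follow-up complete = 100 × 5/A.

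| | A = 8 | A = 7 |
|---|---|---|
| Exposed | 75.0 | 85.7 |
| Not yet treated | 25.0 | 14.3 |
| 30-day follow-up complete | 62.5 | 71.4 |

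**Step 3. Sensitivity of the exposed number.**

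- Linearly rising accrual, 100 × (6/A)²: 56 (A = 8) or 73 (A = 7).
- Linearly falling accrual, 100 × [1 − (1 − 6/A)²]: 94 or 98.
- Slower even accrual: 100 × 6/9 = 67 at 9 months, 100 × 6/12 = 50 at 12 months, 100 × 6/18 = 33 at 18 months.

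**Step 4. What the event-count pause can do earlier.** It needs a third event. The binomial probability of at least 3 events, by true combined event rate, is:

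| True rate | By patient 50 | By patient 75 |
|---|---|---|
| 3% | 0.19 | 0.39 |
| 5% | 0.46 | 0.73 |
| 10% | 0.89 | 0.98 |

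The count acts early when the rate is high. It is often silent at 3% to 5%, although the pulmonary embolism and deep vein thrombosis rates cited in section 5c sum to only 0.17% + 0.07% = 0.24%.

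**Step 5. Reviews tied to enrolment.** The review of n patients at day 30 falls at month n × A/100 + 1, and the number treated by then is n + 100/A.

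| Patients at day 30 | Month (A = 8; A = 7) | Treated (A = 8; A = 7) |
|---|---|---|
| 25 | 3.0; 2.75 | 37.5; 39.3 |
| 50 | 5.0; 4.5 | 62.5; 64.3 |
| 75 | 7.0; 6.25 | 87.5; 89.3 |

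A 75-patient review would come later than month 6 and protect fewer patients (about 11 to 13), so it adds nothing over the present schedule. The 25- and 50-patient reviews do add protection.

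**The case against.** The strongest reply is that the scheduled meetings are only one part of the monitoring plan. The event-count pause and the general pause can both act on any day. The general pause has no fixed count, so it could cover a cluster too small for the event count, such as two events in the first 20 patients. This stands. A reader might infer that there is no safety check before month 6, and the documents do not support that.

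A reader might also infer that such a cluster could not reach the DSMB before month 6. That would be an inference from silence, since nothing bars earlier contact with the board. What remains is that the plan names no route or timing for such contact and does not link either pause to DSMB review.

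The 8 months is a forecast, and neither the accrual pattern nor the start of the review clock is stated. The range of 75 to 86 is therefore conditional, and slow accrual would lower it. This also stands, although the count of one review during treatment needs only the planned duration and the start of the clock.

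Early reviews may also have little to see. With 25 patients, the probability of no thromboembolic event is 0.9976^25 = 0.94 at the cited 0.24%, and 0.971^25 = 0.48 at the upper figure of 2.9% in section 5c. This limits the expected yield, but an early review is there for the case where the rate is higher than expected.

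Finally, a review after treatment has ended is ordinary close-out. The month-12 meeting is not a fault in itself; it simply cannot affect exposure.

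**Conclusion.** The point holds for the scheduled DSMB reviews. On the plan's own timeline one of them falls during treatment, and the next follows the treatment of all patients. With even accrual and a clock from first surgery, the month-6 review would find about 75 to 86 of 100 patients exposed and could protect about 14 to 25. The exposed number is about 56 to 98 under linearly rising or falling accrual, and 50 if accrual takes 12 months.

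The point does not show that the monitoring plan as a whole cannot act for most participants, because both pause provisions can operate earlier. The weakness is narrower: independent review is scheduled late for a trial of this length, and the earlier mechanisms have no stated link to it. Correcting this is a cheap improvement, not the repair of a fatal flaw.

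**What to change.** In sections 5c and 9:

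- Replace the fixed 6-month interval with DSMB reviews tied to enrolment, for example when 25 and 50 patients have reached day 30. On the planned timeline with A = 8, these fall at about months 3 and 5, with about 38 and 63 patients treated. The milestones are an example; the documents prescribe none.
- Keep the month-6 review only as a backstop if those milestones have not been reached by then.
- State that each deep vein thrombosis, pulmonary embolism or seizure is forwarded to the DSMB when the study team learns of it.

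Leave the pause threshold and the board's membership as they are. The cost is protocol wording and about one extra short meeting of the existing three-member board (two reviews during treatment in place of one). No extra patients or procedures are needed.

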There is a large body of evidence supporting the use of tranexamic acid to reduce perioperative blood loss and need for transfusion in trauma, orthopedic, and cardiac surgery.⁷⁻¹¹ Within the field of plastic surgery, previous research has focused on craniomaxillofacial surgery, though there have been preliminary studies of tranexamic acid's utility in burn surgery and aesthetic surgery.^{6,13} Though virtually all authors endorse the integration of tranexamic acid into clinical practice based on their findings, there have been few adequately powered randomized studies in plastic surgery.^{14,15} Furthermore, the majority of prior studies utilized primary outcome variables of unclear clinical significance. In a 2015 randomized controlled trial of 30 patients undergoing reduction mammoplasty, Ausen *et al* described an average 10 cc decrease in 24-hour drain output from topical TXA-treated breasts compared to contralateral controls, which was found to be statistically significant, but otherwise with uncertain clinical implications.¹⁶ In their discussion, Ausen *et al* write that their study was inadequately powered to determine whether or not tranexamic acid could prevent postoperative hematoma.

This study would be the first randomized controlled trial to evaluate the use of tranexamic acid in reducing the rate of hematoma development in patients undergoing reduction mammoplasty. We plan to expand on the findings of Ausen *et al* by selecting hematoma development as the primary outcome variable. Selecting reduction mammoplasty patients as the study population allows us to evaluate each patient as their own internal control, thereby eliminating potential confounders associated with an increased risk of hematoma, such as hypertension.¹⁴ Moreover, breast procedures have been identified as an independent risk factor for hematoma development compared to trunk, extremity, or facial plastic surgery procedures.³ With the large volume of body contouring surgery at our institution, as well as the higher rates of medical comorbidities associated with hematoma formation present in our patient population, we are uniquely equipped to conduct this study. This innovative study will provide high-level evidence regarding the use of tranexamic acid in plastic surgery in an elegant model.

3) Study Design

a) Study Objectives

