This prior probability is combined with the observed data, the number of observed hematomas under each treatment (a binomial random variable) to yield an estimated posterior probability distribution for each hematoma rate. These estimated rates will be used to estimate the posterior distribution for the relative risk, and its natural logarithm which has the advantage of being approximately normally distributed and less skewed given the low expected hematoma rates.

An illustration of the estimated probability distribution for the natural logarithm of the relative risk is shown (left) under the “alternative” hypothesis that treatment with TXA reduces the rate of hematoma by a relative 50% compared to control based on a sample of 100 patients, the proposed sample size. The distribution is obtained by simulation using 100,000 replications. The sample size of 100 was chosen to ensure a high probability of detecting an efficacy signal (a relative risk of 0.5 or less) should it exist.

Specifically, with a sample size of 100, the probability of estimating a relative risk < 1 , or natural logarithm of the relative risk < 0 (i.e., estimating that treatment with TXA is superior to treatment with control) is approximately 80%, corresponding to an odds of 4:1. This 80% probability corresponds to the frequentist notion of power.

Note that the prior odds (assuming equal rates of hematoma) of observing a relative risk less than one is 1:1. Also, the probability of observing odds of 4:1 in favor of TXA under the assumption of equal hematoma rates using each treatment is approximately 20%. This 20% is a false positive rate corresponding to the frequentist Type I error rate.

We will perform a corresponding frequentist analysis using conditional logistic regression to estimate the odds ratio and corresponding 95% confidence interval for developing a hematoma using TXA compared to control. Our use of a non-informative prior ensures that these results will be consistent with those provided by the Bayesian approach, and thus enhance interpretation of the trial's results. Descriptive statistics, using both numerical and graphical summaries, will be used to describe the sample with respect to demographics, baseline characteristics, and important outcomes.

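### Section 8 hypothesises less total blood loss and fewer transfusions, but blood loss has no outcome or test, and neither can be compared between treatments when every patient receives both

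*Combined protocol and SAP*

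**What the plan says.** Section 8 begins: "We hypothesize that use of topical tranexamic acid will decrease total perioperative blood loss, hematoma formation, and transfusion rates". The outcomes in section 3d are narrower. The primary is "Primary outcome: development of hematoma within 30 days of surgery", and the secondaries are given as "Secondary outcome: incidence of blood transfusion within 30 days of surgery, incidence of deep vein thrombosis, and incidence of pulmonary embolism".

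Section 8b analyses hematoma with a Bayesian model and conditional logistic regression. For the secondary endpoints it plans "generalized linear models used to assess treatment group difference in blood transfusion, incidence of deep vein thrombosis, and incidence of thromboembolic events". The only other analysis that could touch blood loss is descriptive: summaries "will be used to describe the sample with respect to demographics, baseline characteristics, and important outcomes", with the important outcomes not listed.

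Blood loss also appears elsewhere. Section 3a says that patient and surgical factors will be examined for their effect on it, although the bolded hypothesis in the same section leaves it out. Section 4c gives it to patients as part of the study's purpose and as a possible benefit.

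On data, section 7 places a drain on each side and has patients write down their daily output. Section 8a abstracts estimated blood loss, drain removal dates and "drain outputs in the immediate postoperative period". Section 2 cites a 30-patient trial of the same split-breast form that "described an average 10 cc decrease in 24-hour drain output from topical TXA-treated breasts compared to contralateral controls", and reports the result as statistically significant but clinically uncertain.

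**The concern.** Two problems lie under the one sentence in section 8. The first is a mismatch: a treatment effect on blood loss is hypothesised, but it has no definition, outcome or test.

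The second concerns the design and also reaches transfusion, which is a listed secondary outcome. Randomisation assigns sides within a patient, so a treatment contrast exists only for quantities that can be attributed to one breast. Total blood loss and transfusion cannot be.

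As written, the report would either pass over the blood-loss hypothesis or fill it with an analysis chosen afterwards. The transfusion model would need a comparison group that the trial does not contain. Meanwhile a bleeding measure that could be attributed to one breast, drain output, is abstracted without a stated side or time window and has no analysis.

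**Working it through.** **1. Each hypothesised quantity against the plan.**

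| Quantity | Outcome in 3d? | Analysis in 8b? | Can TXA and saline be compared? |
|---|---|---|---|
| Hematoma | Yes, primary | Bayesian model; conditional logistic regression | Yes, by breast |
| Total perioperative blood loss | No | None named | No, patient-level |
| Transfusion | Yes, secondary | Generalized linear model | No, patient-level |

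Sections 7 and 8b give every patient both treatments. The treatment indicator in a patient-level transfusion model is therefore the same for everyone, and its coefficient cannot be estimated. An external comparison could stand in, but section 3d names published rates and historical controls for thromboembolic events only.

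**2. The plan's own power figure.** The plan gives no power for blood loss or drain output. Its one figure, about 80% in section 8b, concerns hematoma. Simulation with 100 patients, 7% versus 3.5% and the stated Beta(0.35, 4.65) prior reproduces it as the average posterior probability that the relative risk is below 1: 0.79 to 0.83, depending on where the 0.30 correlation enters. That figure says nothing about drain output.

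**3. What a paired drain comparison could detect.**

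Inputs from section 2: mean within-patient difference 10 cc, 30 patients, statistically significant. Input from section 8b: 100 patients. Assumptions, because the documents give no SD, p-value or test: a paired t-test at two-sided 5%.

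- Significance requires 10 / (SD/√30) ≥ t(0.975, 29 df) = 2.045.
- Hence SD ≤ 10 × √30 / 2.045 = 26.8 cc, a standardized paired difference of at least 10/26.8 = 0.37.
- Power for n pairs comes from the noncentral t with n − 1 df and noncentrality (difference/SD) × √n. For 100 pairs at the bound this is 0.373 × 10 = 3.73, against a critical value of 1.984.

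Section 8a excludes patients who are lost or have insufficient records, and gives no rate, so a range of n is shown.

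| True difference | SD | Pairs | Power |
|---|---|---|---|
| 10 cc | 26.8 cc | 100 | 96% |
| 10 cc | 26.8 cc | 90 | 94% |
| 10 cc | 26.8 cc | 80 | 91% |
| 10 cc | 26.8 cc | 70 | 87% |
| 7.5 cc | 26.8 cc | 100 | 79% |
| 5 cc | 26.8 cc | 100 | 46% |
| 10 cc | 35 cc | 100 | 81% |
| 10 cc | 40 cc | 100 | 70% |

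**4. How firm the 10 cc is.** At the SD bound, the earlier trial's standard error was 26.8/√30 = 4.9 cc, and its 95% CI reached zero. If 10 cc were the true effect, that trial had about 51% power. Spreading the true effect around 10 cc with that standard error (flat prior) gives an average power of about 79% for 100 pairs and 75% for 80. A smaller p-value in the earlier trial would raise these figures, but the documents report none.

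**The case against.** The best defence is that this is an editing slip. The bolded hypothesis in section 3a, the outcomes in section 3d and the primary objective in section 8b all omit blood loss as a treatment outcome, so deleting one phrase would restore agreement. That is partly right, and the phrase should go. But it does not settle the matter: sections 3a and 4c also speak of blood loss, and the transfusion comparison has no groups whatever the wording of section 8.

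A second defence is that leaving drain output untested was deliberate. Section 2 criticises earlier trials for primary outcomes of unclear clinical meaning, and sections 2 and 3d say this of drain output. That stands as a reason not to make it primary. It does not rule out a secondary outcome.

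A third objection is aimed at the remedy, and it stands. A reader might infer that per-breast drain output is already recorded and that analysing it would test the blood-loss hypothesis. The documents support neither. Recording by side is implied by bilateral drains but not written, and the abstraction item has no fixed window. Drain output is only the postoperative, drained part of blood loss, and the study drug is applied after hemostasis.

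**Conclusion.** The point holds. Section 8 carries a blood-loss hypothesis with no outcome or test, and neither total blood loss nor transfusion can be compared between TXA and saline in this design. Both conclusions follow from the text and need no calculation.

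The case for adding drain output is sound but conditional. A reader might take the 96% to show that the comparison is simply well powered, or that it is the one precise efficacy comparison this sample allows. The documents do not go that far. The figure rests on an assumed two-sided 5% paired t-test in the earlier trial, on the SD bound of 26.8 cc derived from it, and on 10 cc being the true effect. At that bound and with 100 pairs, power is 79% at three quarters of the effect and 46% at half.

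**What to change.** 1. Remove total perioperative blood loss from the treatment hypothesis in section 8, and bring the blood-loss statements in sections 3a and 4c into line with what the trial will measure.
2. In section 8b, withdraw the treatment comparison for transfusion. Report transfusion and estimated blood loss as patient-level description, and word the hypotheses in sections 3a and 8 to match.
3. Add to section 3d one breast-level secondary outcome: 24-hour drain output, recorded by side. In section 8b, analyse the within-patient TXA-minus-saline difference by paired t-test, with mean difference and 95% CI. Call it postoperative drainage, not total blood loss. State how missing drain records are handled.
4. Make these changes before the randomization code is broken. If a power statement is included, give the range above and its assumptions.

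The cost is a side and time-window field in the drain abstraction, some wording and one analysis. Treatment and sample size do not change. The downside is that the protocol itself regards drain output as clinically uncertain, so the result would be supportive only and hematoma remains primary.
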